When subjects first contact the study team, a member of the study team will provide them with a detailed description of the study over the phone or in person. If interested and deemed potentially eligible, a member of the study team will offer to send the informed consent form to the subject. Subjects will be encouraged to call study staff with any questions or concerns they might have prior to their first study visit. Consent will be obtained remotely using the eConsent process on REDcap by a trained research staff member designated by the Principal Investigator as adequately knowledgeable of the risks/benefits of the study and the vulnerability of the study population and capable to critically assess the subject's awareness of these factors. The subject will be encouraged to continue to ask questions and express concerns - if any - to study staff throughout their participation in the study. Enrollment will begin when it is clear that the subject thoroughly understands and e-signs the informed consent form. Testing will only take place once the informed consent form is signed.

V. STUDY PROCEDURES

The study procedures will be carried out remotely using a Zoom Enterprise Partners account or in person.

Eligible subjects will undergo the informed consent process in person, by phone or on Zoom Enterprise with a trained research assistant at the beginning of the baseline testing visit. Once consented, subjects will undergo baseline assessments (visit #1) in person or remotely using Zoom Enterprise and REDcap Survey. After baseline testing, subjects will participate in the Tele-TC intervention, with recommended training sessions at least three times a week, along with two or more supplementary one-on-one live sessions (lasting upwards to 45 minutes) with TC instructors. TC proficiency using wearable sensors will be assessed at visit #1 baseline, at two follow-up assessments (visit #2 and visit #3) at approximately 4 and 8 weeks, and at a final assessment (visit #4) at 12 weeks. A semi-structured qualitative interview will also be performed at visit #1 and #4.

[figure not shown]

Figure 2: Flow Chart of the study.

Below, we provide a detailed description of the study procedures.

1. Remote Screening and Informed Consent (Visit #1A)

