Prior to beginning the consent process, study staff will ensure subjects' eligibility using a brief questionnaire. This, in addition to the phone screening done as part of the recruitment process prior to the first visit, will ensure the eligibility of prospective study volunteers. The phone screening is not only undertaken to allow researchers to confirm the subjects' eligibility, but it is also an opportunity for the volunteer to ask any additional questions they might have regarding the study.

Informed consent will be obtained by trained study staff in person, over the phone or by using Zoom Enterprise and eConsent on REDcap. Study staff will explain all the study procedures, equipment, and the risks associated with them as outlined in the informed consent form (ICF).

The devices will be sent or provided to the subjects after consent. Subjects will be provided among others with two mobile devices and requisite chargers, a tablet travel stand, tripod, two GeneActiv watches, 5 wearable sensors, each of them with elastic bands and with chargers and wires. Of the two mobile devices, one will be used to interact with the developed TC app and the other will be used an extra mobile device and stand for virtual visits and video recording.

2. *Remote Assessments (Visits #1B, #2, #3 and #4)*

At *Visit #1B*, subjects will be instructed in how to use the tablet-based Tele-TC program. The mobile devices and the sensors will be provided to each participant and will be preprogramed with all required software. It is worth emphasizing that, as part of the consent process, all subjects will be asked permission to be videorecorded during the assessments via Zoom Enterprise.

Visits will be divided into two components: 1) clinical assessments and 2) instrumented monitoring of TC performance,

The following clinical assessments will be performed during *Visits #1B and #4*.

The following questionnaires will be provided to the subjects through REDcap Survey with an email link. It will take around 45 minutes to complete all of the questionnaires.

- *Activities Specific Balance Confidence (ABC)*: 16-item self-report measure in which patients rate their balance confidence for performing activities.

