Study staff will use Zoom to communicate with subjects during these visits if done remotely. We hypothesize that data collected over 4 sequential visits will show that the sensor-based estimates of the metrics of adherence, proficiency, and safety developed in Phase I are sensitive to longitudinal changes that take place in response to the interventions. The performance of TC exercises will also be videorecorded and scored using the proficiency metric described in our preliminary studies section to provide a gold standard.

Subjects will be asked to don one Smart GeneActiv watch by ActivInsights* in their wrist to monitor activity during approximately a week after visits #1B and a week before visit #4.

We will ask the participants to send the GeneActiv back to the lab after wearing it. We will be sending another GeneActiv about two weeks before visit #4.

3. TC Training Sessions the Tele-TC Platform (12 weeks)

Study volunteers will participate in a 12-week simplified TC program that we have used in multiple prior clinical studies. In this pilot study, the intervention will be delivered via our platform-based application. All participants will be provided with a tablet with the Tele-TC software installed. The structured intervention, designed for older adults, emphasizes essential TC movements that are easily comprehensible and can be performed repetitively in a flowing manner. The protocol includes up to six core TC movements based on the traditional Cheng Man-Ch'ing's Yang-style short form. Additionally, a complementary set of traditional TC warm-up exercises that focus on loosening the physical body, incorporating mindfulness and imagery into movement, promoting overall relaxation, and coordinating breathing awareness are included. Chairs are used in the

protocol for a subset of seated warm-up exercises, as well as for stability and rest as needed. Participants will be asked to practice the protocol (45-60 min) at home for at least 3 days a week for 12 weeks. In addition to data on practice frequency, duration, protocol adherence and training proficiency being automatically collected through our platform, a weekly REDcap survey will be used to monitor adverse events. The TC program will also include 2 or more live instructional sessions via Zoom with a TC instructor.

4. Remote Monitoring of Falls and Other Adverse Events

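### The first activity-watch week follows Visit #1B and the readable text does not keep Tai Chi practice out of it, so the baseline for change in activity level may include practice

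*Combined protocol and SAP*

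**What the plan says.** All references are to the combined protocol and SAP.

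- **Watch weeks (Section V.2, Remote Assessments).** The watch is worn to "monitor activity during approximately a week after visits #1B and a week before visit #4".
- **Visit #1B (Section V.2).** At this visit "subjects will be instructed in how to use the tablet-based Tele-TC program". Participants also perform Tai Chi with the platform while wearing the sensors.
- **Start of training (Section V, opening text).** "After baseline testing, subjects will participate in the Tele-TC intervention, with recommended training sessions at least three times a week". The same paragraph adds live teaching to the home sessions, namely "two or more supplementary one-on-one live sessions (lasting upwards to 45 minutes) with TC instructors".
- **Visit timing (same text).** Proficiency is "assessed at visit #1 baseline, at two follow-up assessments (visit #2 and visit #3) at approximately 4 and 8 weeks". The last of the four visits, Visit #4, is placed at week 12.
- **Practice (Section V.3).** Home sessions last 45–60 minutes, on three or more days weekly, over twelve weeks. The platform records practice frequency and duration automatically.
- **Analysis (Section VI).** Activity level is one of the exploratory outcomes analysed as change between baseline and post-intervention. PASE is a separate item in the same list.
- **PASE (Section V.2).** It asks about the preceding 7 days and is given with the Visit #1B and Visit #4 questionnaires.

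The readable text gives no date for the first home or live session, does not name the event that starts the 12 weeks, and does not ask participants to hold practice during the first watch week. "Figure 2: Flow Chart of the study" is captioned in Section V, but the figure itself is not shown.

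**The concern.** A baseline for a change outcome should precede the intervention. Here the first watch week opens after the visit at which the app is taught, and nothing in the readable text closes that week before practice begins. If a participant starts training straight away, the outcome compares the first programme week with the last one, not a pre-training week with the last one.

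Two consequences follow if practice falls in that week.

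- The measured change in total activity is too small by whatever practice the first week contained.
- The two physical-activity measures have different baselines. PASE completed around Visit #1B looks back before the visit, while the watch looks forward from it. At Visit #4 both cover the week before. A disagreement between the two changes could then reflect timing alone.

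Physical activity is named in Aim 4, and Section VI intends the exploratory results to help power later studies. A pre-training watch week that was not collected cannot be recovered afterwards.

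**Working it through.** The plan states no figure for this outcome, so there is nothing to reproduce. The check has two parts: the calendar, and the practice minutes at issue.

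**1. Calendar**

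Inputs: a watch week of about 1 week after Visit #1B (V.2), 12 weeks of practice (V.3), and visits at about 4 and 8 weeks and at 12 weeks (V, opening text).

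| Weeks counted from | Watch week free of practice? | Result |
|---|---|---|
| Visit #1B | No, practice starts at once | 12 practice weeks fit before Visit #4; overlap with the watch week |
| Visit #1B | Yes | 12 − 1 = 11 practice weeks before Visit #4 |
| First session | Yes | all 12 weeks fit; Visit #4 is 12 + 1 = 13 weeks after #1B |

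The opening text of Section V lists the follow-up weeks in one series with the baseline visit, which suits counting from Visit #1B. The order of headings in Section V (assessments, then training) and the baseline wording in Section VI suit counting from the first session. The text does not choose.

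**2. Practice minutes**

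Let
- m = minutes per session, 45–60 (V.3);
- n₁ = sessions in the first watch week;
- n₁₂ = sessions in the second watch week;
- f = net share of session time that the watch registers as added activity (assumed, 0 to 1).

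Practice part of the measured change = f × (n₁₂ − n₁) × m.

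With a practice-free baseline it would be f × n₁₂ × m.

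Difference = −f × n₁ × m, whatever n₁₂ is.

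With f = 1, and n₁₂ = 3 for the last column:

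| n₁ | Minutes in the baseline week | Share of the practice part of the change lost |
|---|---|---|
| 0 | 0 | 0% |
| 1 | 45–60 | 1/3 = 33% |
| 2 | 90–120 | 2/3 = 67% |
| 3 | 135–180 | 3/3 = 100% |

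Three sessions equal 135/7 = 19 to 180/7 = 26 minutes per day.

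Sensitivity to f at n₁ = 3: f = 0.5 gives 67.5–90 minutes; f = 0 (practice fully displaces equal activity) gives 0. Three sessions is the recommended minimum, not a ceiling: four would give 4 × 45 = 180 to 4 × 60 = 240 minutes at f = 1.

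These are practice minutes, not accelerometer units, because the plan defines no metric for activity level.

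**3. Correlation with adherence**

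The shift is −f × n₁ × m per participant. If it is the same for everyone, it subtracts a constant and leaves any correlation unchanged. It alters the correlation only if first-week practice varies with adherence.

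**The case against.** The strongest case against is that the visible text can be read harmlessly. Training comes after baseline testing, activity level is listed among outcomes collected at baseline, and the watch is described under assessments, before the training heading. On that reading the watch week is part of baseline testing. The missing flow chart may show exactly this. The week-12 wording concerns proficiency assessments and does not say that weeks are counted from Visit #1B.

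Much of this stands. It rules out a claim that the baseline is contaminated, but it does not remove the ambiguity. The opening text of Section V equates the baseline assessments with visit #1, and Section V.2 puts the watch after that visit. Staff who follow both sentences could start practice the next day.

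Three stronger readings are tempting and are not supported:

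- **That overlap will occur.** The text permits it and does not require it.
- **That the correlation with adherence is necessarily weakened.** This needs first-week practice to vary with adherence, which the documents do not address. It is also unclear that the planned correlations cover the watch: Section VI ties them to clinical assessment outcomes, and the watch is described apart from the clinical assessment list in Section V.2.
- **That the watch supply is contradictory.** Section V.1 lists "two GeneActiv watches" among the equipment supplied after consent. Section V.2 has one worn and returned and another sent before Visit #4. That is two watches, both after consent, and Section V.1 does not say they travel together.

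It is also fair to say that the consequence is small. Any overlap would most likely understate a gain in total activity, so it would not create a false one.

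**Conclusion.** The concern holds as an unresolved order of events, not as a demonstrated error. The readable text allows the baseline watch week to contain from 0 to about 135–180 minutes of Tai Chi at the recommended minimum.

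The conclusion rests on these assumptions:

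- activity level in Section VI is the watch measure, which the documents imply but do not state;
- Figure 2 does not already fix the order;
- for the upper figures, three first-week sessions, full registration by the watch and no displacement of other activity.

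The severity is minor. The outcome is one of many exploratory measures in a single-arm feasibility study of 30 participants, Section VI puts conclusive correlation analyses out of scope, and the primary outcomes (retention, protocol adherence and the System Usability Scale) are unaffected.

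**What to change.** **Preferred.** Reconcile the opening text of Section V with Section V.2 so that the first watch week is collected before the first home or live Tele-TC session. State the event from which the 12 weeks are counted. If Figure 2 already shows this, repeat it in the text. This concerns when the baseline is measured and takes no view on how much participants should practise. The cost is a text edit and up to about one week of delay per participant. No extra watch is needed, since two wear periods are already planned.

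**If the schedule is kept.**

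- Label the outcome as change from the first to the last programme week.
- Use the platform logs and the live-session dates to flag anyone who practised in the first watch week.
- Add a supporting analysis that excludes logged session time from both watch weeks.

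The cost is a text edit and a little analyst time. It depends on session logs being time-stamped, which the protocol does not state and the team should confirm. It does not recover a pre-training baseline.

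Under either option, say in Section VI that activity level comes from the watch, if that is what is meant.

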As a preliminary step toward designing a future study to assess the clinical benefits of the Tele-TC platform as a training system, we herein propose to assess:

- If the system enables monitoring longitudinally of adherence, proficiency, and safety;

- If the system is acceptable and user-friendly for its intended use in the home setting;
- As an exploratory aim, if a 12-week training program using the Tele-TC platform leads to improvements in balance, physical activity, self-efficacy, health-related quality of life, and gait.

If this preliminary study leads to positive results, we will embark on a follow-up study to assess the potential clinical benefits of using the technology as part of a clinical intervention on balance, physical activity, self-efficacy, health-related quality of life, and gait.

II. SPECIFIC AIMS

The overall goal of the study is to test the delivery of a novel Tele-Tai Chi (TC) intervention in a single-arm feasibility study for community-dwelling TC-naïve older adults (N=30 total). We will assess feasibility and acceptability measures of the Tele-TC intervention and its specific components through both qualitative and quantitative feedback, as well as the systematic tracking of adherence data to inform future trials and potential clinical use of the Tele-TC system. We will also explore changes in clinically relevant outcome measures including physical activity, self-efficacy, quality of life, balance, gait, and evaluate changes in TC proficiency.

We will pursue the following specific aims:

Primary aims

Aim 1: *To evaluate the feasibility, acceptability, and safety of a novel home-based Tele-TC intervention by tracking recruitment, retention, adherence, and adverse events.*

Hypothesis 1: We will be able to recruit 30 older adults and limit withdrawals to 20% or less.

Hypothesis 2: Participants will complete >60% of recommended Tele-TC sessions.

Hypothesis 3: Protocols for assessing safety can be developed and reliably administered, and preliminary evidence will support Tele-TC can be delivered safely.

Exploratory aims

Aim 2: *To evaluate changes in the level of proficiency of TC during a 12-week simplified TC program using the Tele-TC platform at home.*

Hypothesis 1: We will be able to collect reliable data on TC proficiency during Tele-TC use by study participants.

Hypothesis 2: Proficiency scores will improve over 12 weeks of training using the Tele-TC program.

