We will monitor falls during the subject's participation in the intervention study. Falls will be defined as any event in which the participant unintentionally comes to rest on the ground or other lower level, not as a result of a major intrinsic event or an overwhelmingly external hazard. Falls will be systematically monitored in two ways. As part of our safety and adverse events (AE) monitoring, participants will be asked to complete a weekly REDcap adverse events survey about their TC practice and activities of daily living. Study staff will follow-up by phone with participants as necessary. During study visits #1b-#4, study personnel will inquire about and record characteristics and details of falls and other adverse events.

5. Feedback from the Subjects

During the last visit (visit #4), we will conduct a semi-structured qualitative interview to gather feedback from the subjects regarding the feasibility and acceptability of the study overall, and more specifically the usability of the Tele-TC platform. We will ask them to provide us with feedback regarding general characteristics of the platform, possible improvements of the system, and whether they would consider using the system on a daily basis at home. The qualitative interview will be audiorecorded. In addition, at the end of the study, we will use an adapted version of the System Usability Scale (SUS).

6. In Lab Assessments (Visits #1b and #4)

Subjects will be asked if they are willing to perform a lab testing at baseline and post-intervention visits (#1 and #4) in the Motion Analysis Laboratory (MAL) at Spaulding Rehabilitation Hospital (SRH). Lab visits will include the same battery of assessments utilized in the remote visits, as well as the Mini Balance Evaluation System (Mini BEST) Test. The lab visits will include instrumented monitoring of TC performance as well. The miniBEST is a shortened version of the Balance Evaluation System Test (BESTest). It is a 14-item test scored on a 3-level ordinal scale. It aims to target and identify different balance control systems. The sessions will be videotaped, and the miniBEST test may be instrumented.

7. Return of devices

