The subjects will be asked to return the devices (mobile devices, sensors, tablet stands) in a prepaid and addressed box by mail after the completion of the study. The final payment for the study (\$50) will be contingent on the return of the study equipment. Those that come into the lab for their final testing visit will be asked to return the devices in person.

VI. BIOSTATISTICAL ANALYSIS

The primary outcomes of the study are the retention and the protocol adherence during the study, and the System Usability Scale collected post-intervention.

The exploratory outcomes will include the following:

- The ease of use of the Tele-Tai Chi platform measure with the qualitative interview collected post intervention.
- The changes in outcomes collected at baseline and post-intervention: the Activities-specific Balance Confidence (ABC) scores, PROMIS 29 scores, the Physical Activity Scale for the Elderly (PASE), the Trail Making Test A/B scores, Self-Efficacy Exercise (SEE) scores, the Timed-Up-and-Go, the Timed-Up-and-Go dual task single leg stance, the Sit-to-Stand performance, the balance on both legs with feet shoulder-width apart, the balance on both legs with feet close to each other, the normalized-to-height stride length and stride time variability, the activity level, and the Mini-Balance Evaluation Systems Test (MiniBEST) collected only in individuals who are willing to be tested in the MAL
- The changes in The Tai Chi proficiency scores collected at baseline, 4 weeks, 8 weeks, and pos-intervention.

Descriptive statistics will be derived for all the above-described clinical assessment outcomes and correlations will be sought with the sensor-based estimates of the metrics of adherence, proficiency and safety derived using the previously developed algorithms. Exploratory statistical analyses will be performed to power future clinical studies aimed to test the relationship between the proposed metrics of adherence and proficiency and the clinical outcomes of the intervention. Whereas conclusive statistical analyses to explore such correlations are beyond the scope of the proposed project, the data collected in this pilot study are expected to provide justification for a future trial aimed to assess the efficacy of the Tele-TC Platform as a training system.

VII. RISKS AND DISCOMFORTS

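### Home-session adherence, a primary outcome, has the platform under evaluation as its only named source, so sessions not done cannot be separated from sessions not recorded

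*Combined protocol and SAP*

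**What the plan says.** Section I lists as the first question for this study: "If the system enables monitoring longitudinally of adherence, proficiency, and safety". The same section calls the platform a beta version and argues that the field needs objective measures that can record practice faithfully and confirm it.

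Adherence is also an endpoint. Section VI states: "The primary outcomes of the study are the retention and the protocol adherence during the study", with usability as a further primary outcome. Section II, Aim 1, Hypothesis 2 sets the criterion: "Participants will complete >60% of recommended Tele-TC sessions". Section V, item 3 asks participants to practise "at home for at least 3 days a week for 12 weeks".

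For the data source, section V, item 3 names the platform alone: "data on practice frequency, duration, protocol adherence and training proficiency being automatically collected through our platform". Three other records exist, and none is assigned to check the log:

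- **Weekly survey.** Section V, item 4: "participants will be asked to complete a weekly REDcap adverse events survey about their TC practice and activities of daily living". Its stated purpose is adverse events; no session count is mentioned.
- **Visit video.** Section V, item 2 says that it will be "scored using the proficiency metric described in our preliminary studies section to provide a gold standard". That is a reference for proficiency, at the visits.
- **Wrist watch.** It records general activity for about a week after Visit #1B and a week before Visit #4.

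Section V, item 2 also hypothesises that "data collected over 4 sequential visits will show that the sensor-based estimates of the metrics of adherence", proficiency and safety respond to change over time. Section VI plans descriptive statistics and correlations with clinical outcomes. It plans no comparison of the adherence log with another record.

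**The concern.** The instrument that measures the primary outcome is itself the object of evaluation. A low recorded figure has two possible explanations: participants did not practise, or they practised and the platform did not record it. In a feasibility study these call for different responses, namely changing the programme or repairing the system. The planned data do not tell them apart.

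The error would also carry forward, because section VI intends the adherence and proficiency metrics to help power later trials.

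The four-visit hypothesis leaves a related gap. How often someone practises at home between visits cannot be seen at a visit.

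**Working it through.** The protocol gives no accuracy figure, logging-failure rate or power calculation for adherence, so there is no figure of its own to reproduce. The arithmetic below only shows how sensitive the criterion is.

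**Inputs from the protocol**
- Minimum recommended sessions: 3 per week × 12 weeks = 36 (section V, item 3; the total is derived).
- Criterion: more than 60% (section II). 0.60 × 36 = 21.6, so at least 22 sessions, and 22/36 = 61.1%.

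**Assumptions**
- A share f of completed sessions is not logged. The documents give no value; the range used is 0 to 30%.
- Unlogged sessions count as missed. The protocol does not say this; it is what would happen by default if no rule were added.

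**Formulas**, with t the true adherence:
- recorded = t × (1 − f)
- true adherence needed to record 60% = 0.60 / (1 − f)
- loss that brings t down to 60% = 1 − 0.60 / t

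| Assumed loss f | True value needed to record 60% | True 65% recorded as | True 70% recorded as |
|---|---|---|---|
| 5% | 63.2% | 61.75% | 66.5% |
| 10% | 66.7% | 58.5% | 63.0% |
| 15% | 70.6% | 55.25% | 59.5% |
| 20% | 75.0% | 52.0% | 56.0% |
| 30% | 85.7% | 45.5% | 49.0% |

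Loss that brings the recorded value down to 60%:
- true 65%: 1 − 0.60/0.65 = 7.7%
- true 70%: 14.3%
- true 75%: 20.0%
- true 80%: 25.0%

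**One participant.** The protocol does not say whether the criterion applies to a group mean or to each person. On the per-person reading, with independent sessions, the number logged is binomial with n = 36 and probability t(1 − f). For t = 70%, the chance of logging at least 22 is 0.91 with no loss, 0.66 at 10% loss, 0.49 at 15% and 0.33 at 20%. For t = 80% the corresponding values are 0.998, 0.95, 0.86 and 0.71.

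**The opposite error.** A session logged but not practised raises a participant's recorded figure by 1/36 = 2.8 percentage points. The net direction of bias is therefore unknown.

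**The case against.** The strongest reply is that the trial tests a programme delivered through an app. Hypothesis 2 counts Tele-TC sessions, so practice without the app arguably falls outside it, and a session lost to a technical fault may fairly count against feasibility. This stands in part. It is a reason to state how such sessions are counted. It does not help with an app session that ran but left no record.

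A second reply is that the algorithms come from Phase I and may already have been validated. The protocol refers to a preliminary studies section that is not among the documents, so this cannot be judged here. It would not show how the beta system records unsupervised sessions in this study.

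A third reply is that self-report is weak and that disagreement would not show which source is wrong. That is correct, and it limits the survey to a cross-check. Asking separately about all sessions and about sessions with the app and sensors would still help to locate the discrepancy.

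Three stronger readings are tempting, and the documents do not support them:

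- **A reader might infer that logging failures are counted as missed sessions.** The protocol is silent on this.
- **A reader might infer that the first question cannot be answered.** That question asks whether longitudinal monitoring is enabled, not whether it is correct. Capture over 12 weeks can be described from the logs; accuracy cannot.
- **A reader might infer that adherence cannot vary at the visits because staff direct the session.** Section V, item 2 says that participants follow the platform's instructions. Adherence to the movements within a session may well vary.

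**Conclusion.** The point holds as a gap in measurement. Home-session adherence rests on one source, the system under evaluation, and neither an independent record nor an agreement analysis is planned. The study can report whether logs were captured. It cannot separate non-practice from recording failure at home, or show that the adherence record is accurate.

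The size is conditional. If unlogged sessions count as missed, a loss of 7.7% is enough to bring a true 65% down to the threshold, and a true 70% needs 14.3%. At true adherence of 80% or more, only a loss of 25% or more would matter for a group figure. These rates are assumptions, and they cover one direction of error only. The case for acting rests mainly on the low cost of the repair, not on evidence that the platform fails.

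**What to change.** 1. Add two items to the weekly REDCap survey: the number of Tai Chi sessions done in the past week, and how many of these used the app and sensors.
2. Report the weekly difference and the agreement between log and survey.
3. Repeat the 60% summary with survey-reported app sessions as a sensitivity analysis.
4. State what counts as a completed session and how app sessions lost to technical failure are counted.
5. At Visits #1B to #4, compare logged exercises and duration with the video already recorded, as a check on within-session recording.
6. Assess the practice-frequency part of adherence from home-session data. Within-session protocol adherence may still be assessed at the visits.

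The cost is two survey questions, a short rule and a small descriptive analysis, including some work to read durations from existing video. No new visits are needed. The downside is recall error: the survey is a cross-check on the log and should not be presented as a gold standard.
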